### 5.2 Demographic data

All the analyses in this section shall be performed for the controlled, uncontrolled and total populations.

The descriptive statistic (Mean, SD, Median, Q1, Q3, Min, Max) will be shown for the following continuous variable:

- Age (calculated on the date of the baseline visit)

The categorical variables to be described are: N and (%):

- Age (>=75 years, 65-<75 years, and <65 years)
- Gender
- Race
- Work status
- Life status

### 5.3 Non-valvular atrial fibrillation

All the analyses in this section shall be performed for the controlled, uncontrolled and total populations.

The descriptive statistic (Mean, SD, Median, Q1, Q3, Min, Max) will be shown for the following continuous variables:

- Time since diagnosis, calculated as the time from date of diagnosis to the date of the baseline visit

## **REQUOL Study**

- Age at date of diagnosis
- Time since treatment initiation, calculated as the time from the treatment start date to the date of the baseline visit
- Time during which the patient has not been controlled, calculated as 100-TTR% (Rosendaal method)

The categorical variables to be described are: N and (%):

- TTR% (Rosendaal method): TTR < 65%, TTR >=65%
- TTR% (direct method): TTR < 60%, TTR >=60%
- Type of NVAf
- Current type of anticoagulant medication
- Specify VKA

## **6 DESCRIPTIVE ANALYSIS. UNCONTROLLED PATIENTS**

### **6.1 Physical examination**

The descriptive statistic (Mean, SD, Median, Q1, Q3, Min, Max) will be shown for the following continuous variables:

- Weight
- Height
- BMI

### **6.2 Blood tests**

The descriptive statistic (Mean, SD, Median, Q1, Q3, Min, Max) will be shown for the following continuous variable:

- Creatinine clearance. A single variable will be created for the creatinine clearance value. The auto-calculated creatinine value will be used if available; otherwise the auto-calculated value will be imputed according to the collected creatinine value.

### **6.3 Ejection fraction**

The descriptive statistic (Mean, SD, Median, Q1, Q3, Min, Max) will be shown for the following continuous variable:

- Quantitative-LVEF

The categorical variable to be described is: N and (%):

## REQUOL Study

- Qualitative-LVEF (Normal ( $\geq 50\%$ ), slightly depressed (49-31%), moderately (40-31%), severely ( $\leq 30\%$ ))

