## **9.3 VARIABLES**

The following variables will be obtained at the unique study visit if available in patient medical records:

Variables	Study visit
Informed consent	X
Selection criteria	X
Date of visit	X
Demographic data: age, sex, race, work status, life status, weight, height	X

Variables	Study visit
Non Valvular Atrial Fibrillation (NVAF) history: age at diagnosis, disease duration	X
Concomitant diseases	X
Physical examination: height, weight and BMI	X
Creatinine clearance calculated via Cockcroft-Gault Formula / Creatinine values if available from already existing lab report (to be calculated in eCRF)	X
Left Ventricular Ejection Fraction (LVEF)-quantitative	X
LVEF-qualitative Normal ( $\geq 50\%$ ), slightly depressed (49-31%), moderately (40-31%), severely ( $\leq 30\%$ )	X
TTR	X
CHA 2 DS 2 VASc score (to be calculated in the eCRF)	X
HAS-BLED score (to be calculated in the eCRF)	X
VKA treatment	X
Time since treatment initiation	X
Time since patient is uncontrolled	X
Concomitant treatments	X
Frequency of visits to the physician	X
History of thromboembolic and bleeding events	X
HRQoL questionnaire (Sawicki)	X

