#### **9.3.2.2 Secondary outcomes**

The secondary outcome is the uncontrolled patient profile and will be defined by the following variables collected from patient medical records: demographic characteristics (age, gender, work status, life status, etc), CHA2DS2-VASc, HAS-BLED, AF diagnosis date, VKA treatment, time since treatment initiation, time since patient is uncontrolled (if assessable) left ventricular ejection fraction, Kidney function (creatinine clearance), concomitant diseases, concomitant treatments, frequency of visits to the physician, and history of thromboembolic and bleeding events.

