## **9.9 LIMITATIONS OF THE RESEARCH METHODS**

This study is only descriptive and is not designed to allow for causal inference regarding the impact of OAC control on HRQoL.

Apart from inherent limitations of observational studies, a criticism could be the use of a specific questionnaire of HRQoL originally designed for patients receiving oral anticoagulation with vitamin K and that could ignore other aspects related to quality of life in atrial fibrillation as previously reported

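### The qualitative LVEF bands overlap: a value of 31-40% counts as both slightly and moderately depressed, so the split between those two rows is undefined

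*SAP*

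**What the plan says.** The variables table in Protocol 9.3 lists LVEF twice, once as a number and once as a four-level category. Normal is 50% or more and severe is 30% or less. The levels between them are printed as "slightly depressed (49-31%), moderately (40-31%), severely". SAP 6.3 repeats the same limits, with the middle levels again given as "slightly depressed (49-31%), moderately (40-31" per cent.

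SAP 6.3 summarises "Quantitative-LVEF" as a continuous variable and reports the category as counts and percentages ("The categorical variable to be described is: N and" per cent).

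LVEF is a named part of the secondary outcome, the profile of uncontrolled patients. Protocol 9.3.2.2 lists "left ventricular ejection fraction, Kidney function (creatinine clearance") among its variables, and SAP 8.2 states that the analyses of SAP section 6 meet that objective.

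**The concern.** A table of counts and percentages by category needs each patient to belong to exactly one row. As printed, the slight band runs from 31 to 49 and the moderate band from 31 to 40, so a patient at, say, 35% meets both definitions. The limits stand in the list of variables to collect and in the analysis specification, so they are working definitions and not background text.

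No other rule settles the matter. The documents do not say whether the site ticks the category or the platform derives it from the number. If it is ticked, the approximately 50 centres may label the same value differently. If it is derived, the result depends on which condition is tested first. SAP 6.2 says how two sources of creatinine clearance are to be combined, but SAP 6.3 has no such rule for the two LVEF fields. The rule in SAP section 4 for contradictory entries covers screening criteria only.

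At stake is the division between slightly and moderately depressed function in the description of uncontrolled patients.

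**Working it through.** The plan states no figure to reproduce. The check assigns each whole-number LVEF from 0 to 100 to every band whose printed limits contain it.

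| Category | Printed limits (Protocol 9.3 and SAP 6.3) | Whole-number values | Values also in another band |
|---|---|---|---|
| Normal | 50 or more | 50 to 100 | none |
| Slightly depressed | 31 to 49 | 49 - 31 + 1 = 19 | 10 (31 to 40) |
| Moderately depressed | 31 to 40 | 40 - 31 + 1 = 10 | 10 (31 to 40) |
| Severely depressed | 30 or less | 0 to 30 | none |

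1. **Overlap.** The 10 values from 31 to 40 satisfy two definitions. No value is moderate only.

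2. **Effect on the rows.** Let k be the number of patients at 31-40%. Because no value is moderate only, the moderate row can hold anything from 0 to k patients:
   - if the slight condition is coded first, the moderate row is empty;
   - if the moderate condition is coded first, it holds all k;
   - if sites tick the category, it may hold any number between.

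   The slight row moves by the same amount in the other direction, so the sum of the two rows does not change.

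3. **Size.** The documents give no LVEF distribution. Assume that 5% to 20% of the 170 planned uncontrolled patients (Protocol 9.5) lie at 31-40%: 0.05 × 170 = 8.5, about 9; 0.20 × 170 = 34. The moderate row could then read anywhere from 0% up to 5% at the low end of the assumption, or from 0% up to 20% at the high end. LVEF is collected only where the medical record has it, so the number with any LVEF entry may be below 170.

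4. **Candidate correction.** With the slight band ending at 41, every whole number from 0 to 100 falls in exactly one category, with no overlap and no gap.

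5. **Decimals.** As printed, a value such as 30.5 or 49.5 falls in no band. Ending the slight band at 41 opens a third gap, for example at 40.5. Contiguous limits (50 or more; above 40 and below 50; above 30 up to and including 40; 30 or less) close all three gaps and agree with step 4 at every whole number.

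**The case against.** The strongest reply is that this is a typing slip with little consequence. The bands descend in order, one wrong lower limit explains the whole defect, and most readers would guess 41%. LVEF is also collected as a number, so a patient with a recorded value of 31-40% can be reclassified in the analysis. Where the record holds only a verbal description, the numerical limits play little part. The eCRF is not among the documents, so nothing shows that its screen prints these limits. The category is one row group in a secondary profile, and Protocol 9.9 says of the whole study: "This study is only descriptive and is not designed to allow for causal inference".

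Most of this stands, and it limits the point. A reader might infer that the LVEF results as a whole cannot be interpreted. The documents do not support that: normal, severe, the combined 31-49% group and the continuous summary are all sound. Nor do they show that sites will label patients inconsistently; they show only that sites may. It would also go too far to say that every patient without a numeric LVEF is beyond correction. That applies only where a site applied the faulty limits to a number or range that was never entered, and the documents give no means of sizing that group.

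The reply does not remove the overlap. The same limits appear in both documents, Protocol section 5 records no amendment, and an analyst who follows SAP 6.3 literally still has no rule for 31-40%.

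**Conclusion.** The point holds as a definition error of limited reach. The overlap is certain from the text and needs no assumption: 10 of the 19 whole-number values in the slight band, and all 10 in the moderate band, are doubly classified. The result at risk is the split between slight and moderate in the profile of uncontrolled patients. Group allocation, study size and the primary outcome do not use this variable.

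The number of patients in the overlap is unknown. The range of about 9 to 34 rests on an assumed 5-20% of 170 and on LVEF being available for all of them. A reader might take it as a count of misclassified patients, but it counts patients whose value would fit both bands, and any of them with a recorded number can be placed correctly. That the slight band was meant to end at 41% is the evident reading, not something the documents state.

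**What to change.** - **Protocol 9.3, SAP 6.3, and the eCRF if it carries the same label:** make the four bands mutually exclusive. The sponsor should confirm the intended lower limit of the slight band; 41% leaves the other three printed bands unchanged.
- **SAP 6.3:** add a derivation rule. Where quantitative LVEF is recorded, derive the category from it with contiguous limits: normal at 50 or more; slight above 40 and below 50; moderate above 30 up to and including 40; severe at 30 or less. Use the site's category only where no number exists.
- **Timing:** correct the label before data collection and settle the derivation rule before database closure. SAP 3.1 does not allow the database to be re-opened for inconsistencies found in a results table unless contractual conditions change.

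The cost is one corrected limit in each place where it appears and one derivation line in the SAP. No extra data are needed.

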### 6.4 CHA2DS2VASc

The descriptive statistic (Mean, SD, Median, Q1, Q3, Min, Max) will be shown for the following continuous variable:

- CHA2DS2VASc score: The score is calculated according to the following algorithm.

Variable	Score if answer is "Yes"
Congestive heart failure	1
Hypertension	1
Age $\geq 75$ years	2
Diabetes mellitus	1
Stroke/TIA/Thromboembolism	2
Vascular disease (history of myocardial infarction, peripheral artery disease or aortic plaque)	1
Age 65-74	1
Female sex	1

N and (%) will be presented for the following categorical variable:

- CHA2DS2VASc score (Low risk (score=0), intermediate risk (score=1), high risk (score  $\geq 2$ ))

### 6.5 HAS-BLED

The descriptive statistic (Mean, SD, Median, Q1, Q3, Min, Max) will be shown for the following continuous variable:

- HAS-BLED score, where the score is calculated according to the following algorithm.

Variable	Score if answer is "Yes"
Hypertension	1
Impaired renal function	1
Impaired hepatic function	1
Prior history of stroke = Stroke/TIA	1
Labile INR	1
History of or predisposition to bleeding	1
Age > 65 years	1
Pro-haemorrhagic drugs	1
Alcohol	1

N and (%) will be presented for the following categorical variable:

- HAS-BLED score (Low risk (Score <3), high risk (score  $\geq 3$ ))

## **REQUOL Study**

### **6.6 Thromboembolic events**

The categorical variables to be described are: N and (%):

- Has the patient ever suffered a thromboembolic event?
- List of presented thromboembolic events

### **6.7 Haemorrhagic events**

The categorical variables to be described are: N and (%):

- Has the patient ever suffered a haemorrhagic event?
- List of presented haemorrhagic events
- Severity of haemorrhagic events

### **6.8 Frequency of visits to the doctor**

The descriptive statistic (Mean, SD, Median, Q1, Q3, Min, Max) will be shown for the following continuous variable:

- Number of visits to internal medicine specialist per year

### **6.9 Comorbidities**

The categorical variables to be described are: N and (%):

- Present at least one of the diseases contained in the CRF
- Each of the diseases contained in the CRF
- For each disease, how many are still active

### **6.10 Concomitant treatments**

The categorical variables to be described are: N and (%):

- Treatment
- Indication

## **7 ADVERSE EVENT**

All the analyses in this section shall be performed for the controlled, uncontrolled and total populations.

The categorical variables to be described are: N and (%):

## **REQUOL Study**

- Number of patients who present at least one adverse event
- Number of patients who present at least one serious adverse event
- Number of patients who present at least one adverse event related to Pradaxa®
- Number of patients who present each of the collected adverse events
- A list of serious adverse events will be presented
- A list of adverse events related to Pradaxa® will be presented

## **8 ANALYSIS OF THE OBJECTIVES**

### **8.1 Primary objective**

***To describe HRQoL in uncontrolled patients treated with VKA and controlled patients treated with VKA or DOAC.***

All the analyses in this section shall be performed for the controlled, uncontrolled and total populations.

Quality of Life shall be based on the patients' assessments, by completing the Sawicki questionnaire during the single study visit. This questionnaire includes 32 items grouped in 5 dimensions: overall treatment satisfaction, self-efficacy, strained social disturbances, daily hassles and distress. The highest scores show less quality of life (validated adapted Spanish questionnaire). The response options for each question are: 1=Not at all, 2=Very slightly, 3=Slightly, 4=Moderately, 5=Quite a lot, 6=Very much. The responses correspond to a quantitative scale from 1 to 6.

Reference: Sanchez GR, Yanes BM, Cabrera MA, Ferrer Garcia-Borras JM, Alvarez NR, Barrera LE. [Cross-cultural adaptation of a questionnaire for measuring the quality of life of patients taking oral anticoagulants]. *Aten Primaria* 2004;34(353):353-9.

The categorical variable to be described is: N and (%):

- Number of patients who completed the questionnaire

The summary score for each dimension is calculated by dividing the total score of the items that comprise each dimension by the number of items included in that dimension (arithmetical mean of the items in question).

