Study design:	
This observational multicenter and cross-sectional study will be conducted in Departments of Internal Medicine from approximately 50 centers in Spain
 
Approximately 500 patients seen in internal medicine are planned to be included in the study. To minimize selection bias at the patient level, consecutive patients from each site who meet entry criteria will be enrolled. The 3 participating autonomous communities planned are Madrid, Valencia and Andalucía. Patients should be included in a ratio 2:1, 2 patients controlled (VKA patients with a Time in Therapeutic range TTR ≥ 65% and all DOAC patients) per 1 patient uncontrolled (VKA patients with a TTR < 65%), due to the controlled patients comprise more treatments.
 
Control will be considered when INR values are between 2 and 3.
 
The design of the study impose an only visit to be performed that will
		

	
coincide with one of those performed by the patients as part of routine follow-up of their disease, without interfering with usual clinical practice of the investigator. A specific therapeutic strategy has already been assigned based on routine practice, and without interference with the physician's prescription habits. The observational nature of the study is ensured as no diagnostic or therapeutic intervention outside of routine clinical practice will be applied.

Population:	
Patients with non-valvular atrial fibrillation who are on the same anticoagulant therapy (VKA or DOAC) during at least 6 months and maximum 2 years will be included.
 
The patient will be considered included when he/she agrees to participate in the study by signing the informed consent.
 
The patient will be classified between controlled or uncontrolled group depending on the %TTR if VKA patients. If the %TTR collected from the analytical records was obtained by the Rosendaal method, VKA patients with a TTR < 65% will be allocated to the uncontrolled group and VKA patients with a TTR ≥ 65% will be allocated to the controlled group). If the %TTR was obtained by the direct method, the patient will be considered uncontrolled or controlled depending on whether the TTR value is < 60%. All DOAC patients will be allocated to the controlled group.

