## **7. RATIONALE AND BACKGROUND**

Atrial fibrillation (AF) affects 1-2% of general population, but specially persons between 80 - 85 years, in whom the prevalence can reach 16% [1-3]. The first oral anticoagulants to prevent the risk of thromboembolic events in AF were the vitamin K antagonists (VKA) warfarin and acenocoumarol. The management of these agents remains problematic because they need routine coagulation monitoring, clinical surveillance and continuous patient education, affecting to their daily habits and in consequence to their quality of life [4]. Also, data show that 80% of patients continue receiving acenocoumarol in Spain, with a percentage of International Normalized Ratio (INRs) in therapeutic range between 44%-59% [5,6], and mean time in therapeutic range (TTR) of 64% [5].

The direct oral anticoagulants (DOAC) maintain the benefits of anticoagulant therapy and may increase perception of quality of life among patients because they not necessitate the strict monitoring required for VKA. On the other hand maintaining a stable level of anticoagulation with DOACs prevents uncontrolled patients as well as the increased number of monitoring visits for this reason. Theoretically, this fact would have positive implications in quality of life. However, the available evidence from the study of quality of life, does not suggest that patients have large decrements in their quality of life because of suffering from FA. In this sense, the study of Roalfe et al., cross sectional in 1762 patients over 75 years and suffering AF, concluded that in absence of comorbidity, chronic AF has little impact on generic QoL [7]. This suggests that treatment strategies should focus on the prevention of complications such as stroke, so it is necessary to go depth in the study of the anticoagulant therapy and the impact in QoL.

HRQoL was assessed in a sub-group of the overall RE-LY population to measure the effect of the choice of anticoagulant during a stable phase of treatment in the first year of the study, in patients without outcome events, such as strokes or major bleedings [8]. HRQoL was assessed using the EQ-5D, a generic measure of health outcome. Over the course of one year, all anticoagulated patients without outcome events had stable HRQoL. Scores between dabigatran and warfarin were comparable. There is a dearth of evidence regarding HRQoL in controlled and uncontrolled patients on oral anticoagulants.

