The present study has been designed to describe the HRQoL in patients with non valvular AF receiving conventional VKA but no controlled and those controlled who received VKA or DOAC.

Since the type of patients to be included in this study is that seen in Internal Medicine, i.e. elderly patients, chronically ill, mostly hospitalized, polymedicated, and at high thromboembolic and bleeding risk, the present study will provide valuable data about the HRQoL of these patients regarding their anticoagulation status (controlled or non-controlled).

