### 9.2 SETTING

Approximately 500 patients seen in internal medicine are planned to be included in the study. To minimize selection bias at the patient level, consecutive patients from each site who meet entry criteria will be enrolled. Patients should be included in a ratio 2:1, 2 patients controlled (VKA patients with a TTR  $\geq$  65% and all DOAC patients) per 1 patient uncontrolled (VKA patients with a TTR < 65%), due to the controlled patients comprise more treatments.

The patient will be classified between controlled or uncontrolled group depending on the %TTR if VKA patients. If the %TTR collected from the analytical records was obtained by the Rosendaal method, VKA patients with a TTR < 65% will be allocated to the uncontrolled group and VKA patients with a TTR  $\geq$  65% will be allocated to the controlled group. If the %TTR was obtained by the direct method, the patient will be considered uncontrolled or controlled depending on whether the TTR value is < 60%. All DOAC patients will be allocated to the controlled group. [See figure 2 below.](#)

Figure 2. Patient allocation

If %TTR is not available on analytical records, investigator will calculate it using the last 6 months INR values (at least 4 INR values during the last 6 months). To perform the calculation, it is recommended to avoid periods of anticoagulation initiation and periods with treatment interruptions due to surgery or bleedings.

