### **9.7.1 Main analysis**

The primary outcome of the study is the health-related quality of life as measured by the Sawicki questionnaire. The scores of each individual question will be summarized descriptively in the controlled and uncontrolled patients. In addition, the summary score for each dimension of the questionnaire will be calculated for each patient by dividing the total score by the number of items included in that dimension and summarized in the same way as the individual questions.

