#### **2.2 Primary study objective**

To describe HRQoL in uncontrolled patients treated with VKA and controlled patients treated with VKA or DOAC.

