**The analyses will be performed with the eligible patients.**

# REQUOL Study

## 5 DESCRIPTIVE ANALYSIS.

### 5.1 Groups

The number of controlled vs uncontrolled patients shall be described.

The allocation of each patient to each group is performed automatically by the platform where the data are collected during the study and is performed at the time the VKA and TTR data are collected.

Patients receiving AVK and TTR (Rosendaal method) <65%, or TTR (direct method) <60% are assigned to the uncontrolled group. The rest of the patients are assigned to the controlled group.

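### The HRQoL tables have no controlled-VKA or DOAC column, so the controlled column mixes control status with drug class and the limitations section does not say so

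*SAP*

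**What the plan says.** The primary objective (SAP 2.2, with the same content in protocol section 8) is: "To describe HRQoL in uncontrolled patients treated with VKA and controlled patients treated with VKA or DOAC". For the analysis, protocol 9.7.1 says: "The scores of each individual question will be summarized descriptively in the controlled and uncontrolled patients". It treats the dimension scores in the same way. SAP 8.1 adds a total column: "All the analyses in this section shall be performed for the controlled, uncontrolled and total populations".

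The groups are set in protocol 9.2 and SAP 5.1. A VKA patient is uncontrolled if TTR is below 65% (Rosendaal method) or below 60% (direct method). SAP 5.1 then says: "The rest of the patients are assigned to the controlled group". Protocol 9.2 is explicit on the other drug class: "All DOAC patients will be allocated to the controlled group". It also gives the wider range of treatments among controlled patients as the reason for the 2:1 recruitment ratio.

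SAP 5.3 counts the current type of anticoagulant by group. No HRQoL summary in SAP 8.1 uses that variable, and item 10.3 of the ENCePP checklist (protocol Annex 2) marks stratified analyses as not applicable. Protocol 9.9 disclaims causal inference about anticoagulation control and notes that the questionnaire was designed for VKA patients. It does not mention that the controlled group combines two drug classes.

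**The concern.** The word controlled carries two meanings within one column. For VKA patients it is the result of a TTR classification; for DOAC patients it follows from the drug they take. The neighbouring uncontrolled column contains no DOAC patients. The two columns therefore differ in control status and in drug class at once.

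Protocol section 7 says the study will inform about HRQoL by anticoagulation status, so readers will look at these two columns for that purpose. The same section gives a reason why drug class could matter: it says DOACs "may increase perception of quality of life among patients because they not necessitate the strict monitoring required for VKA". The instrument is sensitive to that burden. Of the six Treatment Satisfaction items listed in SAP 8.1, four (4, 12, 15 and 21) ask about time spent on control, waiting for results or time lost at the doctor's. At stake is whether the primary tables can be read as a description of control status at all.

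**Working it through.** **Inputs from the documents.** About 330 controlled and 170 uncontrolled patients (protocol 9.5), about 50 centres (protocol 9.1), items scored 1 to 6 (protocol 9.3.2.1). The documents give neither the DOAC share of the controlled group, w, nor expected scores, SDs or an intra-centre correlation (ICC). All of these are assumptions below.

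**The plan's own precision figures.** Table 9.5: 1 gives Clopper-Pearson 95% interval widths at 10, 20, 30, 40 and 50% prevalence. Recomputed:
- n=170: 9.59, 12.54, 14.27, 15.20, 15.50 (stated 9.60, 12.54, 14.27, 15.20, 15.50).
- n=330: 6.77, 8.91, 10.16, 10.83, 11.05 (stated 6.78, 8.91, 10.16, 10.84, 11.05).

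Every cell agrees to within 0.01 point. The table covers only the two group totals; nothing is stated for parts of the controlled group.

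**What the columns contain.** By identity:

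pooled controlled mean = (1 − w) × controlled VKA mean + w × DOAC mean

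So controlled minus uncontrolled = (controlled VKA − uncontrolled VKA) + w × (DOAC − controlled VKA). The first term is the difference by control within VKA. The second is a drug-class term weighted by w, which is neither planned nor capped.

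**Size of the second term.** Set the first term to zero and assume a class difference of 0.5 points. The columns then differ by w × 0.5: 0.05 at w=10%, 0.25 at 50%, 0.45 at 90%.

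**What the two printed means cannot separate.** Assume an uncontrolled mean of 3.0 and a pooled controlled mean of 2.8.

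| w | If controlled VKA = 3.0, DOAC = (2.8 − (1 − w) × 3.0)/w | If DOAC = 3.0, controlled VKA = (2.8 − w × 3.0)/(1 − w) |
|---|---|---|
| 20% | 2.00 | 2.75 |
| 50% | 2.60 | 2.60 |
| 80% | 2.75 | 2.00 |

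In the middle column there is no difference by control within VKA. In the right-hand column DOAC patients score the same as uncontrolled VKA patients, and the whole difference lies within VKA. The printed means are identical in both. SAP 5.3 would reveal w but not which case holds.

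**Precision if the column is split.** The 95% half-width of a mean in SD units is 1.96/√n with independent, complete responses. With clustering it is multiplied by √(1 + (n/50 − 1) × ICC), assuming patients are spread evenly over 50 centres. The n=66 row is the smaller part at w=20% or 80%; n=165 is an even split.

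| n | Independent | ICC 0.05 | ICC 0.10 |
|---|---|---|---|
| 66 | 0.241 | 0.243 | 0.245 |
| 165 | 0.153 | 0.161 | 0.169 |
| 330 (pooled) | 0.108 | 0.122 | 0.135 |

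**The case against.** The strongest reply is that the pooling was chosen and disclosed. The objective names the controlled group as VKA or DOAC, the allocation rule is explicit in both documents, and SAP 5.3 will show the drug mix. Protocol 9.9 disclaims causal inference and checklist section 3 says no measure of association is produced. All of this stands. A reader might infer that the SAP departs from the protocol, that a comparison is biased, or that the mix is concealed; the documents support none of these. What the reply does not supply is the display. A disclaimer about causality does not tell a reader that the controlled column also encodes drug class.

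Further points stand in part:
- A reader might say HRQoL is never shown for a single drug class. That goes too far: the uncontrolled column is VKA only. What is missing is a controlled-VKA column and a DOAC column.
- The abstract says: "Control will be considered when INR values are between 2 and 3". This could be taken to mean that DOAC patients breach the study's own definition of control. It can equally be read as the therapeutic range underlying TTR, so it does not show an inconsistency.
- Protocol section 7 also reports comparable dabigatran and warfarin scores in a RE-LY sub-study. That used the generic EQ-5D rather than this questionnaire, but it is a reason not to presume a class difference.
- The protocol's contents list has a blank entry after 9.3.2.2, so removed text cannot be excluded. The SAP contents list only 8.1 and 8.2 under the objectives, with no HRQoL analysis by drug class.
- Controlled VKA is itself mixed, since it combines two TTR methods with different cut-offs. Splitting by class does not remove that.
- A DOAC column invites an unadjusted drug comparison on a VKA-designed instrument. This is a genuine cost and needs a caveat beside the column.

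**Conclusion.** The point holds as a limit on interpretation. From the planned tables, a difference between controlled and uncontrolled patients cannot be attributed to control status among VKA patients rather than to drug class. The identity behind this needs no assumption. The sizes do: the 0.05 to 0.45 points rest on an assumed class difference of 0.5 and on w between 10% and 90%, and the 3.0 and 2.8 example is purely illustrative. These figures show that the two explanations cannot be separated, not that a class effect is likely or how large it would be. It would be wrong to conclude that drug class will drive the result. The change is a worthwhile and inexpensive improvement; its absence would not invalidate the study.

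**What to change.** In SAP 8.1, add descriptive columns for controlled VKA and for DOAC beside uncontrolled VKA, and keep the pooled controlled and total columns. State that the uncontrolled-VKA and controlled-VKA columns are the within-class, unadjusted description of control status, with no test.

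In the limitations, state that the pooled controlled column mixes control status with drug class. State also that the DOAC column must be read with the VKA-designed questionnaire and differences in prescribing in mind. Update checklist item 10.3, because columns by drug class are a form of stratified description. The checklist statement that no measures of association are performed is unaffected.

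The cost is SAP wording, two table columns and a short limitation text. Anticoagulant type is already collected, and no extra patients or change of objective is needed. The downside is longer tables and less precise columns: a half-width of about 0.15 SD at n=165 and 0.24 SD at n=66, against 0.11 SD pooled. With an assumed ICC of 0.05 to 0.10 these become 0.16 to 0.17, 0.24 to 0.25 and 0.12 to 0.13 SD. Keeping the pooled columns means no planned precision is lost.
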